Sample Size Estimates: Power and sample size for the study proposal is fixed due to the expected number of eligible patients to be recruited into this pilot study during the study window. Based on preliminary data and the described definitions of types of infection, investigators anticipate that over a 1-year recruitment window they will be able to enroll approximately 10 individuals with no fungal infection, 10 patients with a fungal infection but not ABPA and 5 with ABPA. The primary analysis plan focuses on the description and comparison of key plasma and sputum measures described in Table 3. Power analysis provides the detectable effect sizes when comparing the control arm (no fungal infection) to either the non-ABPA group or the ABPA group. Calculations are based on a power of 80% and Type I error rate of 0.05 for two-sided two-sample equal-variance t-test conducted in PASS version 15 statistical software (2). Group sample sizes of 10 and 5 in the fungal infection groups achieve 80% power to reject the null hypothesis of zero effect size when the population effect size is 1.36 and 1.66 respectively. Thus, the study is powered at 80% to detect a difference in the mean markers to be measured greater than 1.66 and 1.32 standard deviations. Given limited data in the literature regarding Th2 markers in CF, we are basing these calculations off of deviations from a mean for the multiple Th2 markers we are testing.

Study Visit: We plan to prospectively recruit 25 subjects with CF during a period of clinical stability. Subjects will have one research clinic visit that will coincide with their clinic visit at CHCO Pulmonary Clinic facilities. The following diagnostic information will be entered onto Case Report Forms: demographic information, diagnostic history and mutations, CF-related co-morbidities, historic microbiology results including fungal culture results, medications including modulator therapy and long-term antibiotic regimens, previous allergy testing, diagnostic criteria for ABPA (if applicable). We will also utilize historical clinical data from the medical record to establish other co-morbidities, lung function trends and baseline, history of other bacterial infections, history of allergy diagnoses, and other pertinent medical history and diagnostic testing (ie previous CT scan results, previous blood work, etc.). The following evaluations will be performed (Table 2, Figure 2):

- Historical data in the medical record

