Rationale: Studies have shown increased rates of atopy, asthma, and fungal allergen sensitization in adults with CF, yet the impact of this is not clearly understood^{14, 15}. There have been few studies in pediatrics with little understanding of when this sensitization develops and the changes in outcome measures that may be the result of a more allergic airway in the setting of CF. Furthermore, ABPA is a known severe condition that individuals with CF can develop, yet the timeline and predisposition that patients face is unclear. Given this, allergic sensitization to fungal elements in the environment may be playing a reactive role in the CF airway and provide clues to the development of ABPA, asthma, and other pulmonary sequelae.

Study Design and Visit: Described fully under specific aim 1, discussing patient criteria, inclusion, and study operations. Serum ImmunoCAP samples will be collected under the same blood draw as described in the study design. Specific panel to be collected described in Table 4.

Statistical Analysis: Will utilize descriptive statistics and associations of each group as well as differences between groups. Will utilize a biostatistician to help with data analysis, organization, and reporting.

Specific Aim 1: Compare Th2 inflammation in patients with and without fungal infections in patients with CF.

- Individual markers: We will use descriptive statistics to measure the differences between each individual marker in both the sputum and serum between groups. We will further look at associations with serum and sputum measurements in each group.
- Clinical and Environmental characteristics: We will use descriptive statistics to account for differences and associations in lung function and BMI between groups. We will also account for differences in individuals by other co-infections (*Pseudomonas*, MRSA, etc.) in our analysis and study these associations as well. Given that ABPA individuals will be harder to recruit, we will do our best to control based upon individuals recruited into this group.

This is a pilot and discovery study searching for possible Th2 markers to further study and use clinically. Given this, our goal is to detect as many possible markers as we can feasibly study and thus why we will not initially be correcting for multiple comparisons.

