Specific Aim 2: Investigate allergic sensitization to fungal elements in patients with CF fungal infection without ABPA compared to those without fungal infection and those with ABPA.

- Serum ImmunoCAP measurements: We will use descriptive statistics to measure the differences and associations between each individual mold reaction between groups.
- Immune Profile: After each individual marker is analyzed, the questionnaire is assessed, and clinical characteristics are described, we will attempt to use this information develop a “profile” describing a panel of serum/sputum markers, allergic sensitization measurements, clinical characteristics, and other findings consistent with each group of subjects in association with their type of fungal disease.

Shapiro-Wilks tests will be used to assess for normality of the distributions of measured outcomes. Basic descriptive statistics will be presented in tabular form as mean ± standard deviation, median [inner-quartile range; min and max] and frequency (percent). ANOVA regression models will assess for overall between group differences and estimate the least-squared differences for all pairwise comparisons after evaluating the jackknife studentized residual plots. If residuals suggest violations to modeling assumptions, namely heteroscedasticity of variance, Breslow-Day tests will be conducted to confirm unequal variance across groups. Welch’s T-test will be used in the presences of un-equal variance. If evidence of non-normality of residuals exists, either Box-Cox transformations of the outcomes or non-parametric approaches such as Wilcoxon rank sum will be used to compare groups when evidence of non-normally distributed outcomes exists. For dichotomous outcomes, Fisher’s Exact tests will be used to compare groups. As the study is

hypothesis generating, statistical significance will be set at an alpha 0.05 level for both overall and pairwise comparisons. All analyses will be conducted in either R studio or SAS statistical software 9.4 (1).

Outcome Measures:

Primary outcome: Difference in sputum Th2 biomarkers (ECP, IL4, IL5, IL10, IL13, and eosinophil count) in patients with CF with fungal infection with expected elevation of sputum Th2 biomarkers in patients with CF and ABPA compared to those without fungal infection and without ABPA (Table 3).

Secondary outcomes:

- Serum Th2 biomarkers in patients with fungal infection and ABPA (Table 3).

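### Serum-sputum associations are planned only within groups of 10, 10 and 5, where estimates are very imprecise; a pooled, group-adjusted estimate should be added beside them

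*Combined protocol and SAP*

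**What the plan says.** The Statistical Analysis section opens with a general statement: "Will utilize descriptive statistics and associations of each group as well as differences between groups". Under Specific Aim 1, Individual markers, it adds: "We will further look at associations with serum and sputum measurements in each group". It names no coefficient, test, confidence interval, target correlation or power for this step.

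Sample Size Estimates expects to enrol "10 individuals with no fungal infection, 10 patients with a fungal infection but not ABPA and 5 with ABPA". Its only power statement concerns differences in means: "Calculations are based on a power of 80% and Type I error rate of 0.05 for two-sided two-sample equal-variance t-test".

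The ANOVA models described under Specific Aim 2 compare groups. The 0.05 level is also tied to group comparisons: "statistical significance will be set at an alpha 0.05 level for both overall and pairwise comparisons". On multiplicity, the plan states that "we will not initially be correcting for multiple comparisons". No pooled or group-adjusted serum-sputum association appears anywhere.

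Table 3 lists seven soluble markers in both fluids: IL4, IL5, IL10, IL13, ECP, IL8 and interferon-gamma. Associations between the fluids do not appear among the primary, secondary or tertiary outcomes.

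**The concern.** Whether a serum marker tracks its sputum counterpart bears on the study's search for usable biomarkers. Splitting 25 patients three ways leaves each estimate with little information, and in the ABPA group almost any true value is compatible with what will be observed.

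Two things are at stake. An association that is present in all groups may be described too vaguely to be useful. Chance scatter among three noisy coefficients may also be read as a difference between groups. The second risk matters because the plan intends to build an immune profile for each group from its serum and sputum markers. Seven shared markers in three groups give 7 × 3 = 21 coefficients.

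**Working it through.** **Inputs.** Group sizes 10, 10 and 5, two-sided 0.05 and 80% power come from Sample Size Estimates. The documents give no expected serum-sputum correlation, so a range is assumed. Bivariate normality is assumed (for example after a log transformation), with equal marker variances across groups.

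**The plan's own figure.** Exact noncentral-t power for the two-sample t-test, solved for 80%, gives 1.325 SD for 10 against 10 and 1.660 SD for 10 against 5. These match the statement "greater than 1.66 and 1.32 standard deviations". The sentence before it reads "when the population effect size is 1.36 and 1.66 respectively". The 1.36 does not fit 10 against 10, where it would give 82.0% power. That is a separate matter and does not affect this point. Neither figure says anything about correlations.

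**Precision (Fisher z).** The interval is tanh(atanh(r) ± 1.96/√m), with m = n − 3 within a group. For the pooled partial correlation, which adjusts for two group indicators, m = 25 − 2 − 3 = 20. With r = 0.6, atanh(r) = 0.693.

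| Analysis | m | 1.96/√m | 95% interval |
|---|---|---|---|
| n=5 | 2 | 1.386 | -0.60 to 0.97 |
| n=10 | 7 | 0.741 | -0.05 to 0.89 |
| Pooled, group-adjusted | 20 | 0.438 | 0.25 to 0.81 |

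**If the associations were tested.** The observed r needed for p<0.05 is t/√(df + t²):
- n=5 (df 3): 3.182/√(3 + 10.128) = 0.88
- n=10 (df 8): 2.306/√(8 + 5.318) = 0.63
- pooled (df 21): 2.080/√(21 + 4.325) = 0.41

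Power with the same true correlation in all three groups (noncentral t averaged over the distribution of the predictor's sum of squares, with simulation agreeing at the values checked):

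| True correlation | n=5 | n=10 | Pooled |
|---|---|---|---|
| 0.3 | 7% | 13% | 29% |
| 0.4 | 10% | 21% | 49% |
| 0.5 | 13% | 33% | 71% |
| 0.6 | 19% | 49% | 89% |
| 0.7 | 27% | 68% | 98% |

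**Apparent group differences by chance.** With a common correlation of 0.6, all three groups reach p<0.05 with probability 0.486² × 0.185 = 0.04, and none does with probability 0.514² × 0.815 = 0.22. The groups therefore disagree about 74% of the time although nothing differs between them.

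**If the correlations differ by group** (simulated; control, fungal, ABPA):

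| True correlations | Pooled power | Best single group | Serum-by-group interaction (2 df) |
|---|---|---|---|
| 0, 0.6, 0.6 | 40% | 49% (fungal) | 21% |
| 0, 0.7, 0 | 28% | 68% (fungal) | about 30% |
| 0, 0, 0.8 | 11% | 41% (ABPA) | about 17% |

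In these cases pooling loses power, and the interaction test would usually miss the reason.

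**The case against.** The plan promises only to look at associations, in a section framed as descriptive, and its 0.05 level is set for group comparisons. Critical values and power matter only if someone tests these correlations, and the plan does not say that anyone will. This stands, and it is why the case rests on the intervals, which matter with or without a test.

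A reader might infer that almost nothing can be detected within the groups, or that a real association would usually be reported as absent. The documents support neither. No test is named. At n=10, a true correlation of 0.8 would have 87% power. If all three groups were tested at a common 0.6, at least one would be significant about 78% of the time (1 − 0.22), although the chance of at least one false positive under no association is 1 − 0.95³ = 14%.

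A reader might also infer that the pooled estimate should replace the per-group ones. The study's hypothesis is that inflammatory profiles differ between the groups, so a common association cannot be taken for granted, and a single averaged number cannot describe each group. That stands too, and it limits the proposal to an addition.

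Finally, the wording is loose enough that serum-to-sputum association is an interpretation, though the natural one. The study is an exploratory pilot whose size is fixed by recruitment, and no listed outcome depends on this step.

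**Conclusion.** The point holds as a cheap improvement. Per-group estimates alone will be very imprecise, and at n=5 an interval of -0.60 to 0.97 is uninformative. A group-adjusted estimate from all 25 patients uses only within-group variation, so differences in group means cannot create it, and it narrows the interval to about 0.25 to 0.81.

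The interval and power gains rest on roughly similar within-group associations, approximate normality, and paired serum and sputum from all 25 patients. Sputum induction is conditional in the protocol, so some pairs may be missing, which would widen every interval and lower every power shown. Where associations differ by group, the pooled value is an average, and it can be less sensitive than the fungal group alone. The primary comparison is unaffected.

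**What to change.** In the Statistical Analysis section, Specific Aim 1, Individual markers:

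- Keep the per-group serum-sputum coefficients, and report each with a 95% interval as description only.
- Add, for each marker measured in both fluids, one association across all patients with paired samples, adjusted for group. This can be a partial correlation, or a regression of the log sputum marker on the log serum marker plus group. The group adjustment is essential, because without it mean differences between groups can produce a correlation.
- State that the pooled value averages the within-group associations and is most useful when they are similar.
- If a serum-by-group interaction is shown, state that it has only about 17% to 30% power in the scenarios above, so a non-significant result does not show that pooling is valid.

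The cost is a few sentences in the plan and one extra model per shared marker. No new patients, samples or procedures are needed, and nothing now planned is lost.

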Hypothesis: We hypothesize that children with CF and fungal infections without ABPA will have elevated allergic inflammatory profiles and increased sensitization to fungal elements compared to those without fungal infection.

Specific Aims:

- **Specific Aim 1:** Compare Th2 inflammation in patients with and without fungal infections in patients with CF and to those with ABPA.
 - Approach: We will obtain serum and sputum samples from 25 patients with either (1) fungal infection without ABPA, n=10 (defined as \geq two positive fungal cultures in prior 18 months), (2) no fungal infection, n=10, and (3) ABPA, n=5, and measure specific sputum and serum cytokine measurements to evaluate Th2 and Th1 inflammatory pathways.
 - Biomarkers measured: Eosinophilic cationic protein (ECP), Interleukin-4 (IL4), Interleukin-5 (IL5), Interleukin-10 (IL10), Interleukin-13 (IL13), and eosinophil count in both serum and sputum.
 - Expected outcome: Individuals with fungal infection without APBA will have elevated Th2 markers of inflammation compared to those with no fungal infection. We will also compare to those with ABPA as a separate control group. We will also measure Th1 markers to be used as a reference to previously established inflammatory profiles seen in CF, seeing if those with fungal disease deviate towards a more Th2 driven process.
- **Specific Aim 2:** Investigate allergic sensitization to fungal elements in patients with CF fungal infection without ABPA compared to those without fungal infection and to those with ABPA.

- Approach: We will measure total IgE and serum ImmunoCAP testing of specific IgE levels to fungal proteins of various species (*Aspergillus*, *Candida*, etc). to determine fungal sensitization. We will also survey patients regarding environmental exposures to explore relationships with allergic sensitization.
- Expected outcome: Individuals with fungal infection without ABPA will be more likely to show allergic sensitization to fungal elements when compared to those with no fungal infection.

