- Serum Th1 biomarkers in patients with fungal infection and ABPA (Table 3).
- Serum sensitization markers to fungal allergens in patients with fungal infection and ABPA (Table 4).
- Baseline and historic lung function, historical comorbid diagnoses and BMI measurements in patients with fungal infection and ABPA.
- Environmental factors that are possibly related to fungal infection and ABPA in patients with CF.
- Immune profile: A profile of each group will be based upon their findings of each set of biomarkers: Th1, Th2, mold allergy panel, and systemic markers of inflammation. Based upon findings in each of these categories (elevated, depressed), we will be able to formulate a profile based upon the type of marker/inflammatory pathway.

Tertiary outcomes: Banking of both sputum and serum to potentially utilize microbiome and transcriptome techniques for further immunotyping and infection characterization.

Data Collection and Storage: All subjects will be de-identified upon study sample collection and stored with a master key. There will be limited access to this information with the PI and only essential research staff able to monitor and view the data. All hardcopy source documents will be kept in a locked file cabinet in the CF research team's storage facilities. Additionally, to further ensure data integrity, data for this study will be stored in Research Electronic Data Capture system (REDCap), which will allow limited access to only essential personal. REDCap enables in-line validation to minimize transcription errors and provides real-time notifications of data submission and allows immediate central monitoring and feedback. Access to data requires an encrypted secure socket layer (SSL) connection and changes are logged by user ID, time stamp and project. Databases are backed up frequently.

Description, Risks, and Justification of Procedures and Data Collection Tools.

Assessment of Risk:

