Pulmonary Function Testing: Spirometry will be performed according to American Thoracic Society Guidelines¹⁹. The indices measured during the testing include forced expiratory volume in 1 second (FEV1), forced vital capacity (FVC), FEV1/FVC ratio and mid-volume forced expiratory flow (FEF25-75). Our pulmonary function laboratory has been used in a number of studies of CF^{12, 20, 21}. The anticipated risks involved with this procedure are a temporary increase in cough and shortness of breath. To minimize this risk, we will encourage the subject to take big breaths and take breaks between coughing to reduce the tendency to develop gagging or violent coughing. Pulmonary function testing is a part of the standard clinical care for patients with cystic fibrosis.

Blood draw: This will be performed per standard operating procedure of the CHCO clinical and research laboratory sites utilizing patient samples and body fluids. Sterile technique with fresh needles and devices will be used in to minimize infection risk. Trained nursing staff and/or phlebotomists will be the ones performing the blood draw in a CHCO approved environment for proper drawing and handling of specimens. Using these individuals will also minimize the risk for local trauma, bruising, and/or injury that is possible with routine blood draws.

The following testing will be performed on all serum samples:

- **Inflammatory Indices:** Serum samples will be sent to the Core and Clinical Laboratory to measure various systemic markers of inflammation (Table 3) which are thought to reflect clinical parameters in CF. The main markers of Th2 inflammation to investigate are: IL4, IL5, and ECP. The main markers of Th1 inflammation to investigate are: IL8, IFNY, NE-APC.
- **Mold Panel:** A panel of allergic sensitization (IgE levels) to various environmental fungi and molds will be sent on serum samples, along with a total IgE sample (Table 4).
- **Banking of samples to be used for molecular identification of bacteria/fungus and Molecular identification of transcription factors/gene signaling:** All remaining serum and sputum samples will be stored in the appropriate storage device and temperature in the CF research teams designated sample storage area for later analysis utilizing transcriptomics, proteomics, and/or microbiome analysis.

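### For yes/no outcomes, Fisher's exact test is valid but conservative at the planned group sizes; Boschloo's exact test would recover power cheaply, by an amount that depends on true rates and final enrolment

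*Combined protocol and SAP*

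**What the plan says.** The general methods paragraph of the Statistical Analysis section gives one rule for binary data: "For dichotomous outcomes, Fisher’s Exact tests will be used to compare groups". On the level, it says that "statistical significance will be set at an alpha 0.05 level for both overall and pairwise comparisons", and gives the hypothesis-generating purpose as the reason. The Aim 1 analysis text adds that multiple comparisons will not initially be corrected, because the goal is to pick up as many candidate markers as possible.

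Sample Size Estimates expects to "enroll approximately 10 individuals with no fungal infection, 10 patients with a fungal infection but not ABPA and 5 with ABPA". Its power statement concerns means only: "Calculations are based on a power of 80% and Type I error rate of 0.05 for two-sided two-sample equal-variance t-test". No power, event rate or sidedness is given for a binary outcome.

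One secondary outcome contains variables that are yes/no by nature: "Baseline and historic lung function, historical comorbid diagnoses and BMI measurements in patients with fungal infection and ABPA". Fungal sensitisation is less clear. Specific Aim 2 expects that infected patients "will be more likely to show allergic sensitization to fungal elements when compared to those with no fungal infection", which reads as yes/no. The Mold Panel paragraph describes "A panel of allergic sensitization (IgE levels) to various environmental fungi and molds will be sent on serum samples", which is a measured level, and no cut-off for a positive result is given.

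**The concern.** Fisher's test conditions on the total number of positives. In this design only the group sizes are fixed and that total is random. With groups of 10 and 5 few p-values are attainable, so the true false-positive rate can sit far below 0.05. The plan openly accepts an uncorrected 5% per comparison in order not to miss signals, and its sample size is fixed by expected recruitment. A test that spends about a quarter of that 5% at 10 v 10 works against this aim. At stake is power for secondary binary comparisons: 7/10 v 2/10, for instance, has p = 0.070 under the plan and 0.041 under Boschloo's test.

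**Working it through.** **The plan's own figure.** The only power figures are for the t-test. Noncentral-t calculation gives detectable differences at 80% power of 1.325 SD (10 v 10) and 1.660 SD (5 v 10). This matches the printed 1.32 and 1.66; the section also prints 1.36 for 10 v 10. There is no binary figure to reproduce.

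**Inputs.** From the documents: groups of about 10, 10 and 5; level 0.05; Fisher's test. Assumed: two-sided testing, as in the t-test calculation, and all true rates.

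**Size of Fisher's test.** Let R be the set of tables (x of n₁, y of n₂) with two-sided Fisher p ≤ 0.05. With a common rate π,

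size(π) = Σ over R of C(n₁,x)·C(n₂,y)·π^(x+y)·(1−π)^(n₁+n₂−x−y),

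which is largest at π = 0.5.

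- 10 v 10: R contains y=0 with x≥5, y=1 with x≥7, y=2 with x≥8, y=3 with x≥9, y=4 or 5 with x=10, and the mirror images (34 of 121 tables). The sum is 2 × (638 + 10×176 + 45×56 + 120×11 + 210 + 252) = 13,400. Size = 13,400 / 2²⁰ = **1.278%**.
- 5 v 10: R contains y=0 with x≥3, y=1 with x≥4, y=2, 3 or 4 with x=5, and the mirror images (16 of 66 tables). The sum is 2 × (16 + 10×6 + 45 + 120 + 210) = 902. Size = 902 / 2¹⁵ = **2.753%**.

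**Boschloo's test.** Order tables by the two-sided Fisher p-value and take the largest cut-off whose maximum size over all π is at most 5%. R is contained in the new region by construction.

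- 10 v 10: the cut-off is Fisher p ≤ 0.0867. It adds 12 tables (4 v 0, 6 v 1, 7 v 2, 8 v 3, 9 v 4, 10 v 6 and their mirrors), giving 46. At π = 0.5 these add 4×210 + 4×2,100 + 4×5,400 = 30,840, so size = 44,240 / 2²⁰ = **4.219%**.
- 5 v 10: the cut-off is Fisher p ≤ 0.0952. It adds 6 tables, giving 22. Maximum size is **4.9998%**, at π = 0.2854. Two of the six (2/5 v 0/10 and 3/5 v 10/10) have p = 0.049998.

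**Power** = Σ over the rejection region of Bin(x; n₁, p₁)·Bin(y; n₂, p₂).

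| True rates | 10 v 10: Fisher → Boschloo | 5 v 10: Fisher → Boschloo | 5 v 10 without the two boundary tables |
|---|---|---|---|
| 70% v 20% | 42.6% → 62.2% | 33.1% → 53.7% | 52.3% |
| 60% v 10% | 47.4% → 65.9% | 38.9% → 65.3% | 57.3% |
| 80% v 20% | 63.5% → 80.5% | 49.3% → 67.7% | 67.2% |

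**Gain at 10 v 10 by true difference** (all rate pairs from 5% to 95% in steps of 5):

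| Difference (points) | Gain (points of power) |
|---|---|
| 5–10 | 0.7–4.1 |
| 20 | 7–9 |
| 30 | 12–17 |
| 40 | 17–20 |
| 50 | 18–20 |
| 60 | 14–17 |
| 70 | 8–10 |
| 80 | about 3 |
| 85 | 1.0 |
| 90 | 0.2 |

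Outside that grid the gain can reach 25.1 points (40% v 0%: 36.7% → 61.8%). At 5 v 10 it nearly vanishes when both rates are high (95% v 55%: 0.5 points).

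**Gain at nearby enrolments**, for the three scenarios in the power table:

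| Sizes | Gain (points) |
|---|---|
| 10 v 9 or 9 v 10 (fungal v control) | 4–10 |
| 11 v 10 or 10 v 11 | 2–9 |
| 11 v 11 | 8–14 |
| 12 v 10 | under 1 |
| 6 v 10 (ABPA v control) | under 1 |
| 5 v 9 | 0–2 |

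**Cost in false positives.** If the 14 listed allergens were analysed as yes/no with no true differences, worst-case expected false positives would rise from 14 × 1.278% = 0.18 to 14 × 4.219% = 0.59 at 10 v 10, and from 14 × 2.753% = 0.39 to 14 × 4.9998% = 0.70 at 5 v 10. The nominal figure is 14 × 5% = 0.70.

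**The case against.** The strongest reply is that this is a preference between two valid tests, shown at a flattering sample size. Much of that stands. Fisher's maximum size is unusually low at exactly 10 v 10: it is 2.10% at 9 v 9, 2.07% at 10 v 9, 2.72% at 11 v 10 and 3.22% at 12 v 10. One participant more or fewer in a single group at least halves the gain in most of the scenarios. A reader might take 3 to 20 points as a general gain. The documents do not support that, because they give no rates and only approximate enrolment.

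It is also fair that no important endpoint is certain to be binary. The primary outcome is continuous, specific IgE is measured as a level, and much of the clinical description is planned as descriptive. A reader might infer that the sensitisation comparison is being run on a weak test. That holds only if sensitisation is dichotomised, which the plan does not say; levels would follow the ANOVA or Wilcoxon route.

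Finally, software conventions matter. Doubling the smaller one-sided p-value, as scipy does by default, gives 0.066 for 3/5 v 1/10, against 0.035 with the Fisher-p ordering. Doubling agrees at equal sizes, does worse at 5 v 10 (44.0% for 70% v 20%) and better at 10 v 9 (61.7% against 53.7%). So the proposed ordering is not best everywhere.

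What survives is that, with this ordering, Boschloo's test never loses a Fisher rejection and never exceeds the 5% the plan has already accepted.

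**Conclusion.** The point holds as a cheap improvement of low severity. Fisher's test at 10 v 10 and 5 v 10 has a true size of at most 1.3% and 2.75%, and Boschloo's test uses more of the stated 5% without exceeding it. These sizes and the nesting of the rejection regions follow from the group sizes and two-sided testing alone. The power gain rests on assumed rates and on enrolment landing close to plan. Small true differences remain badly underpowered either way (40% v 20% at 10 v 10: 5.8% → 13.1%).

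It would be wrong to read this as an error in the plan, or as bearing on the primary sputum biomarker comparison. What is certain to be affected is secondary yes/no variables such as comorbid diagnoses, where they are tested.

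**What to change.** Replace the Fisher sentence in the Statistical Analysis section with:

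> Pairwise comparisons of dichotomous outcomes will use Boschloo's unconditional exact test, with tables ordered by the two-sided Fisher p-value, at two-sided 0.05; any overall three-group comparison will use the Fisher-Freeman-Halton test.

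If sensitisation is to be analysed as yes/no, state the cut-off for a positive result in the same place.

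The cost is one sentence and a short piece of code, with no new data. R, which the plan already allows, is enough. The downsides are:

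- The test is less familiar.
- The ordering must be set explicitly in software. Check the code against 7/10 v 2/10 (p = 0.041) and 3/5 v 1/10 (p = 0.035).
- At 5 v 10 the maximum over the common rate must be computed precisely, or the two tables at p = 0.049998 are lost.
- The doubled convention does better at some unequal sizes, such as 10 v 9.
- The per-test false-positive rate moves closer to the stated 5%, though it stays within it.

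Make the change before the data are analysed, so that the test is not chosen after seeing results.

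### Does the primary outcome predict the wrong contrast by attaching its expected elevation only to ABPA?

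*Combined protocol and SAP*

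**What the plan says.** The Primary outcome paragraph under Outcome Measures names six sputum markers (ECP, IL4, IL5, IL10, IL13 and eosinophil count). It refers to a difference "in patients with CF with fungal infection with expected elevation of sputum Th2 biomarkers in patients with CF and ABPA", with people who have neither fungal infection nor ABPA as the comparator.

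Under Specific Aims, the Aim 1 expected outcome reads "Individuals with fungal infection without APBA will have elevated Th2 markers of inflammation compared to those with no fungal infection", and then "We will also compare to those with ABPA as a separate control group". The same aim lists its biomarkers as ECP and the four interleukins, "and eosinophil count in both serum and sputum". The secondary outcomes begin with "Serum Th2 biomarkers in patients with fungal infection and ABPA (Table 3".

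In the Statistical Analysis section, the Aim 1 heading stops at "Compare Th2 inflammation in patients with and without fungal infections in patients with CF". The text below it says that "our goal is to detect as many possible markers as we can feasibly study" and gives this as the reason for not correcting for multiple comparisons at first. The models are to "estimate the least-squared differences for all pairwise comparisons", with alpha at 0.05 for overall and pairwise comparisons.

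Sample Size Estimates powers two contrasts with a two-sided t-test: control versus fungal infection without ABPA, and control versus ABPA.

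**The concern.** A primary outcome should tell the reader which result answers the study's question. The question here is whether fungal infection without ABPA carries a Th2 signal. ABPA is the reference condition, in which such a signal is already expected. The sentence gives a direction for the reference condition and none for the contrast of interest. A reader who went no further could take raised markers in ABPA as confirmation of the hypothesis, although that finding would say nothing about fungal infection without ABPA.

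Two nearby labels add to the doubt. Table 3 and the Inflammatory Indices paragraphs single out IL4, IL5 and ECP as priority or main markers. Sample Size Estimates describes a primary analysis plan covering plasma and sputum, whereas Outcome Measures makes sputum primary and serum secondary. With no multiplicity correction, the primary label does much of the work of separating the main result from the exploratory ones. If the label were truly open, the choice of headline result could be made after the data were seen.

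**Working it through.** **1. Do the two statements conflict?** For fungal infection without ABPA versus no fungal infection, Outcome Measures says a difference, and the Hypothesis and Aim 1 say an elevation. For ABPA versus no fungal infection, Outcome Measures says an elevation, and Aim 1 says it will be compared as a further control. An elevation is a difference, so both sets of statements can hold together. Aim 1 completes the primary-outcome sentence; it does not contradict it.

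**2. Is ABPA out of place in the primary outcome?** The Aim 1 heading in Statistical Analysis omits ABPA, but it is a shortened form. The full Aim 1 title, under Specific Aims and again under Experimental Design and Methods, includes the comparison with ABPA. Sample Size Estimates powers that comparison too.

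**3. Do priority and main mean primary?** No. Table 3 also gives priority to NE, IL8 and IL-1B for Th1, and no Th1 marker is in the primary outcome. The serum Inflammatory Indices paragraph calls IL4, IL5 and ECP main in serum, where Th2 markers are a secondary outcome. The labels cut across the outcome ranking, so they do not reduce the six primary markers to three.

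**4. Is the fluid open?** No. Outcome Measures ranks sputum first and lists serum Th2 as secondary. The Aim 1 list covering both fluids says what is measured, not how it is ranked. Plasma in Sample Size Estimates is a loose term for the blood sample, since Table 3 has only a serum column.

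**5. Do the power figures depend on the wording?** Inputs from Sample Size Estimates: groups of 10, 10 and 5, power 80%, two-sided alpha 0.05, equal-variance t-test.

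Power(d) ≈ P(T > t₀.₉₇₅,df), where T is noncentral t with df = n₁ + n₂ − 2 and noncentrality d / √(1/n₁ + 1/n₂); the opposite tail is negligible.

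- 10 vs 10: df = 18, √(1/10 + 1/10) = 0.447. Solving for 80% gives d = 1.325. Power at the stated 1.32 is 79.7%.
- 5 vs 10: df = 13, √(1/5 + 1/10) = 0.548. Solving for 80% gives d = 1.660. Power at the stated 1.66 is 80.0%.

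Both figures reproduce. The same section also prints 1.36 for 10 vs 10, where power is 82.0%; 1.32 is the value that matches 80%. Expected direction is not an input to a two-sided calculation, so rewording the outcome would alter neither figure.

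**6. What does the label cover?** Both contrasts with control: 6 markers × 2 = 12 comparisons. The fungal contrast alone: 6 × 1 = 6. Three groups give 3 pairwise contrasts, so the models produce 6 × 3 = 18 sputum Th2 comparisons at 0.05 under either reading. The 6 and the 12 are subsets of the same 18.

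**The case for a change.** The strongest case for a change is that a primary outcome should stand by itself. In a study that tests everything at 0.05, its wording is what fixes the headline result. Leaving two contrasts unranked, with a direction only for the one that does not test the hypothesis, invites selective emphasis. Rewording would cost one sentence.

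Part of this stands. The sentence is awkward, and it would read better with the Aim 1 direction beside the ABPA expectation. It does not amount to a needed change, for two reasons. First, an outcome measure has to give the variable, the groups and the comparator, and this one does. The expected direction belongs to the hypothesis, where it is stated plainly. Second, the obvious rewording would make ABPA versus control a supporting comparison. That would be more than an edit: it would demote a contrast that the outcome names, the sample-size section powers and the full aim title includes. Whether the two contrasts rank equally is for the investigators to decide, and nothing in the planned analysis depends on it.

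**Conclusion.** The wording is imprecise, but the plan needs no change. An analyst following it as written would fit the same models, estimate the same group differences and obtain the same p-values as under a tidier sentence. The Hypothesis and Aim 1 leave no doubt about which contrast answers the study's question. The effect on detectable differences is nil (1.32 SD and 1.66 SD stand), and the only ambiguity is whether 6 or 12 of the 18 sputum comparisons carry the primary label.

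This rests on three readings of the plan: the analysis tests are two-sided, as in the power calculation; each pairwise contrast is reported for every marker; and no decision rule turns on ABPA elevation, since none is stated. It also relies on the declared status of the study as a hypothesis-generating pilot. In a confirmatory trial with a formal success criterion, the ranking of the two contrasts would have to be settled. The 1.36 beside 1.32, and plasma where Table 3 has serum, are clerical.
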